## 15 REGULATORY CONSIDERATIONS

### 15.1 Protocol Review and Amendments

This protocol, the proposed informed consent and all forms of participant information related to the study (e.g., advertisements used to recruit participants) and any other necessary documents must be submitted, reviewed and approved by a properly constituted IRB governing each study location.

Any changes made to the protocol must be submitted as amendments and must be approved by the IRB prior to implementation. Any changes in study conduct must be reported to the IRB. The MSSM Overall Principal Investigator (or Protocol Chair) will disseminate protocol amendment information to all participating investigators.

All decisions of the IRB concerning the conduct of the study must be made in writing.

### 15.2 Informed Consent

15.3 All participants must be provided a consent form describing this study and providing sufficient information for participants to make an informed decision about their participation in this study. The formal consent of a participant, using the IRB approved consent form, must be obtained before the participant is involved in any study-related procedure. The consent form must be signed and dated by the participant or the participant's legally authorized representative, and by the person obtaining the

CONFIDENTIAL

This document is confidential. Do not disclose or use except as authorized.

consent. The participant must be given a copy of the signed and dated consent document. The original signed copy of the consent document must be retained in the medical record or research file 15.3 Ethics and Good Clinical Practice (GCP)

This study is to be conducted according to the following considerations, which represent good and sound research practice:

- E6 Good Clinical Practice: Consolidated Guidance  
[www.fda.gov/downloads/RegulatoryInformation/Guidances/UCM129515.pdf](http://www.fda.gov/downloads/RegulatoryInformation/Guidances/UCM129515.pdf)
- US Code of Federal Regulations (CFR) governing clinical study conduct and ethical principles that have their origin in the Declaration of Helsinki
  - Title 21 Part 11 – Electronic Records; Electronic Signatures  
[www.access.gpo.gov/nara/cfr/waisidx\\_02/21cfr11\\_02.html](http://www.access.gpo.gov/nara/cfr/waisidx_02/21cfr11_02.html)
  - Title 21 Part 50 – Protection of Human Subjects  
[www.access.gpo.gov/nara/cfr/waisidx\\_02/21cfr50\\_02.html](http://www.access.gpo.gov/nara/cfr/waisidx_02/21cfr50_02.html)
  - Title 21 Part 54 – Financial Disclosure by Clinical Investigators  
[www.access.gpo.gov/nara/cfr/waisidx\\_02/21cfr54\\_02.html](http://www.access.gpo.gov/nara/cfr/waisidx_02/21cfr54_02.html)
  - Title 21 Part 56 – Institutional Review Boards  
[www.access.gpo.gov/nara/cfr/waisidx\\_02/21cfr56\\_02.html](http://www.access.gpo.gov/nara/cfr/waisidx_02/21cfr56_02.html)
  - Title 21 Part 312 – Investigational New Drug Application  
[www.access.gpo.gov/nara/cfr/waisidx\\_02/21cfr312\\_02.html](http://www.access.gpo.gov/nara/cfr/waisidx_02/21cfr312_02.html)
- State laws
- MSSM research policies and procedures

It is understood that deviations from the protocol should be avoided, except when necessary to eliminate an immediate hazard to a research participant. In such case, the deviation must be reported to the IRB according to the local reporting policy.

## 15.4 Study Documentation

The investigator must prepare and maintain adequate and accurate case histories designed to record all observations and other data pertinent to the study for each research participant. This information enables the study to be fully documented and the study data to be subsequently verified.

Original source documents supporting entries in the case report forms include but are not limited to hospital records, clinical charts, laboratory and pharmacy records, recorded data from automated instruments, microfiches, photographic negatives, microfilm or magnetic media, and/or x-rays.

## 15.5 Records Retention

All study-related documents must be retained for the maximum period required by applicable federal regulations and guidelines or institutional policies.

CONFIDENTIAL  
This document is confidential. Do not disclose or use except as authorized.

## 15.6 Multi-center Guidelines

Protocol Chair – [name]

The Protocol Chair is responsible for performing the following tasks:

1. Coordinating, developing, submitting, and obtaining approval for the protocol
2. as well as its subsequent amendments
3. Assuring that all participating institutions are using the correct version of the protocol.
4. Taking responsibility for the overall conduct of the study at all participating institutions and for monitoring the progress of the study.
5. Reviewing and ensuring reporting of Serious Adverse Events (SAE)
6. Reviewing data from all sites, and performing interim analysis as indicated.
8. Initiation of stopping rules at all participating sites if necessary

Coordinating Center- Mount Sinai Health System

The Coordinating Center is responsible for performing the following tasks:

1. Ensuring that IRB approval has been obtained at each participating site prior to the first patient registration at that site, and maintaining copies of IRB approvals from each site.
2. Managing central patient registration
3. Collecting and compiling data from each site.
4. Establishing procedures for documentation, reporting, and submitting of AE's and SAE's to the Protocol Chair, and all applicable parties.
5. Facilitating audits by securing selected source documents and research records from participating sites for audit, or by auditing at participating sites.
6. Providing a protocol appendix for each Participating Site describing the participating site patient population, expertise, and available resources.
7. Coordinating Center personnel and the PI will collect information from the Participating Site and report appropriately to the IRB. Information reported may include but is not limited to adverse events, stopping rule triggers, interim analysis results, study results, unanticipated events related to the study, etc.

Participating Sites

1. Participating sites are responsible for performing the following tasks:
2. Following the protocol as written, and the guidelines of Good Clinical Practice (GCP).
3. Submitting data to the Coordinating Center through ERAP.
4. Registering all patients with the Coordinating Center by submitting patient registration form, and signed informed consent promptly.
5. Providing sufficient experienced clinical and administrative staff and adequate facilities and equipment to conduct a collaborative trial according to the protocol.
6. Maintaining regulatory binders on site and providing copies of all required documents to the Coordinating Center.

CONFIDENTIAL

This document is confidential. Do not disclose or use except as authorized.

## Meetings

Teleconferences of all investigators, research nurses and other study staff involved in the study will take place, starting once both sites have enrolled a subject. The following study team members involved with the conduct of the trial will be included as appropriate: study coordinators, data managers, research nurses, sub-investigators, collaborators (if applicable), and the statistician. The timing of these meetings will be at minimal quarterly, but more frequent during initial accrual, adverse event reporting, or at any time at the discretion of the Participating Site or Coordinating site.

During these meetings, matters related to the following will be discussed: enrollment rate relative to expectation, characteristics of participants, retention of participants, adherence to protocol (potential or real protocol violations), validity and integrity of the data, toxicities, surgical complications, unanticipated barriers, acquisition of serum samples and transfer to lab, and progress of data for objectives. Any other issue related to the trial may be discussed with the Participating Site and the Coordinating Center. Formal minutes of these discussions will be provided to the appropriate personnel, and if applicable, formal action plans.

## 16.0 STATISTICAL CONSIDERATIONS

### 16.1 Study Design/Endpoints

This is a prospective clinical trial evaluating surgery alone for early stage HPV related oropharyngeal squamous cell carcinoma. The primary endpoints are the rate of local-regional control OAS, and PFS at 3 years in patients with HPV 16 and p16+ related head and neck cancer, treated with surgery alone. The secondary objectives include 5 year PFS, LRC, Overall Survival, Ultimate Disease Control, QOL, site of failure and rate of salvage, as well as establishing biomarkers predictive of treatment outcomes and collection of tumor tissue, germline DNA and a plasma bank for future studies. The main study hypotheses is that OAS and UDC at 5 years for surgery alone for early stage HPV related oropharyngeal squamous cell carcinoma is equivalent to current regimens involving standardized post-operative radiotherapy (>85%) and that LRC without radiotherapy will be > 50%. Additional Hypotheses relate to Group 2 and 3 - OAS and PFS at 5 years for reduced dose XRT and CRT intermediate stage HPV related oropharyngeal squamous cell carcinoma is equivalent to current regimens involving standardized post-operative radiotherapy (>85%) and that LRC will be > 85%.

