Studies in unselected patients suggest that patients with HPVOPC have a better prognosis than patients with HPV-negative, predominantly environmentally related OPC (EROPC) . In one retrospective study of radiotherapy as sole therapy from Denmark, p16 was used as a surrogate for HPV. In this randomized study of a radiation sensitizer, the control arm of radiotherapy only was analyzed for p16 expression. There was 62% 5-year survival among p16+ patients compared to 26% in p16- patients. LRC was 58% vs. 28%, respectively (Figure 1). A significant fraction of p16+ tumors were not of oropharyngeal origin .

[figure not shown]
A second trial, Licitra et al retrospectively evaluated surgery in the HPV positive and negative cases. Surgery alone was effective therapy for a small group of patients. Patients who underwent surgery as a single modality were spared the long term consequences of radiation. However, selection criteria for surgery alone was not well explained.

CONFIDENTIAL

This document is confidential. Do not disclose or use except as authorized.

Figure 2: Surgery and HPV in Oropharynx Cancer

Recently, results of retrospective analyses of survival and HPV status were reported from two International Phase III trials comparing chemoradiotherapy (CRT) regimens in locally advanced HNC. In both trials there were insufficient patient numbers to report a treatment effect; however the impact of HPV on survival, regardless of therapeutic assignment, was highly significant . The RTOG (R) 01-29 has the most extensive data and retrospectively analyzed on 323 out of 433 OPC cases. In RTOG 01-29, patients were randomized between CRT with accelerated fractionation with cisplatin versus regular fractionation and cisplatin. The overall survival (OS) and progression free survival (PFS) at three years were 82% and 74% in HPVOPC compared to 57% and 43% for EROPC, respectively. A careful analysis of failure and death revealed a LRF rate of 14% versus 35% for HPVOPC versus EROPC and a second primary tumor rate of 6% versus 15% respectively. Non-cancer deaths also occurred in 9% and 19% respectively. All these data support a better outcome for HPVOPC, much of which is found in improved LRC, some of which is explained by less comorbidity.

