### Pathological Evaluation/Criteria and Post-Operative Treatment Assignments

#### Group I:

- Complete resection (margins: tonsil >1mm, tongue >3mm, pT1-2, pN0-2B),
- No LVI, no PNI, <3 positive nodes.
- No ECS, No matted or Level  $\geq$ III,

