### 16.2 Sample Size/Accrual Rate

Sample size justification:

The proposed sample size of 100 for Group 1 has been determined to ensure that an upper bound for recurrence may be estimated with adequate precision, defined as within 8-12% of the true recurrence rate. The upper bound is estimated by the posterior probability of recurrence given the observed data, assuming a non-informative beta(1,1) prior distribution. The table below provides the upper 95% bound (from the Bayesian credible interval) assuming the true rate of recurrence is .1,.2,.3,.4, or .5 and 100 patients are studied.

True recurrence	Upper 95% bound
.1	.184
.2	.301
.3	.413
.4	.516

CONFIDENTIAL

This document is confidential. Do not disclose or use except as authorized.

[figure not shown]

.5

.614

The various specific aims outlined in Aim 1 share a common objective: determining rates of important measures of treatment response (progression-free survival, overall survival, local regional control and ultimate disease control) for patients treated with surgery alone and compare them to those expected in patients with similar diagnostic criteria. We will assess this overall objective by using a Bayesian approach to estimate the posterior probability distributions for each respective sub-aim based on observed outcomes. This approach permits estimating probabilities with which a specified rate of interest exceeds a threshold value (e.g.; 50% local regional control, 85% overall survival, etc.)

Our approach begins with the premise that surgery alone offers no improvement in expected outcomes. This is an exact correspondence to a "null hypothesis". We incorporate this assumption through a prior distribution for each suspected rate; for example, for Group I patients we would assume that the rate of local regional control (LRC) at three years is 50%. After the studies are conducted, each respective rate is combined with the "null" prior distribution through Bayes' Theorem to yield the posterior distribution for the rate. The table below depicts simulated results for the posterior LRC ( $\theta$ ) using 100 patients based on two differing assumptions: that LRC at three years is 50% ( $p=0.5$  shown on the left) and 85% ( $p=0.85$  shown on the right).

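### Section 16.1 claims equivalence against one unsourced figure, >85%, for groups split by prognosis and for endpoints that differ by definition

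*Combined protocol and SAP*

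**What the plan says.** Section 16.1 states two equivalence hypotheses. The first reads "The main study hypotheses is that OAS and UDC at 5 years for surgery alone for early stage HPV related oropharyngeal squamous cell carcinoma" and continues "is equivalent to current regimens involving standardized post-operative radiotherapy (>85%) and that LRC without radiotherapy will be > 50" percent. The second begins "Additional Hypotheses relate to Group 2 and 3 - OAS and PFS at 5 years for reduced dose XRT and CRT" and names the same comparator, "standardized post-operative radiotherapy (>85%) and that LRC will be > 85" percent. Side by side:

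| Endpoint | Group I | Groups 2/3 |
|---|---|---|
| OAS, 5 years | >85% | >85% |
| UDC, 5 years | >85% | none |
| PFS, 5 years | none | >85% |
| LRC | >50% | >85% |

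Section 16.2 says that surgery-alone rates will be estimated in order to "compare them to those expected in patients with similar diagnostic criteria", and gives 85% overall survival as an example of a posterior threshold. It gives no matched rate, no source and no adjustment.

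Section 5.0 assigns groups after surgery. Group I needs complete resection, no extracapsular spread (ECS), and "No LVI, no PNI, <3 positive nodes". Groups II, IIIA and IIIB are defined by adverse findings. Section 1.0 describes the trial as non-randomized.

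**The concern.** With no randomised or concurrent control, a claim of equivalence is only as good as the external rate it is set against. That rate has to answer one question: what would patients with this pathology have achieved on standard adjuvant therapy? Section 5.0 separates patients by features that the protocol itself treats as prognostic, and Section 16.1 then uses one number on both sides of that split. Nothing shows that it is the expected rate for either side.

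The same number also serves for OAS and PFS in Groups 2/3, and for OAS and UDC in Group I, although these endpoints count different events.

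At stake is the trial's main conclusion, that radiotherapy can be omitted in Group I without loss. As the hypotheses stand, a result above 85% cannot be divided between the effect of treatment and the effect of choosing favourable patients.

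**Working it through.** **1. Can the 85% be traced?** No. No derivation or citation accompanies it, so it cannot be reproduced. In the readable text of Section 2 (its figures are not in the copy reviewed), the nearest overall survival figures are 82% at three years in HPV-related disease after chemoradiotherapy (Section 2.1), and 82% and 80.6% at two years in two transoral robotic surgery series (Section 2.2). None is a five-year rate after postoperative radiotherapy, and none is broken down by the pathology that defines the groups.

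**2. Is it matched to the groups?** From Section 5.0:

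- Group I: clear margins, no lymphovascular or perineural invasion, no ECS, fewer than three positive nodes.
- Group II: close margins, lymphovascular or perineural invasion, or ECS up to 1 mm.
- Group IIIA: three or more nodes, or supraclavicular or contralateral nodes.
- Group IIIB: positive margins, ECS of 1 mm or more, matted nodes, or more than six nodes.

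Section 16.1 sets different LRC thresholds for Group I and for Groups 2/3. It does not do so for OAS, the one other endpoint that both hypotheses share.

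**3. Can one figure serve different endpoints?** Section 11.0 counts progression or death as a PFS event, so at any time t, PFS(t) ≤ OAS(t). UDC requires being alive and disease free, so UDC ≤ OAS as well. With a common floor, PFS above 85% already implies OAS above 85%, and the OAS threshold adds nothing. The one pair the protocol quotes from a single source differs: "The overall survival (OS) and progression free survival (PFS) at three years were 82% and 74% in HPVOPC", a gap of 82 − 74 = 8 points. That is three-year chemoradiotherapy data, so it illustrates the ordering and does not supply a five-year postoperative PFS benchmark.

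**4. How far could a shared figure be off?** This step is illustration only. Assume that 85% were the average over all groups, that Group I were a share s of 30–70% of patients, and that the groups differed by d of 5–15 points under standard care. None of these inputs is in the documents.

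- Group I rate = 0.85 + (1 − s)d. With s = 0.7, d = 0.05: 0.865. With s = 0.5, d = 0.10: 0.900. With s = 0.3, d = 0.15: 0.955.
- Groups 2/3 rate = 0.85 − sd. With s = 0.3, d = 0.05: 0.835. With s = 0.7, d = 0.15: 0.745.

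**5. What would that do to the conclusion?** Take n = 100 for Group I and the beta(1,1) prior from Section 16.2, so that x successes give a Beta(1 + x, 101 − x) posterior. Treat all 100 as evaluable at five years. No success cut-off is stated, so assume success means P(θ > benchmark) ≥ 0.80, borrowing the level of the stopping rule in Section 14.2.

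| Benchmark | Successes needed | Pass probability, true rate 88% | Pass probability, true rate 90% |
|---|---|---|---|
| 85% | 89 | 0.45 | 0.70 |
| 90% | 93 | 0.08 | 0.21 |
| 95% | 98 | <0.001 | 0.002 |

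If the matched benchmark were 95% and surgery alone truly gave 90%, Group I would usually pass at 85% and almost never at 95%. With 90 of 100 observed, the posterior probability of exceeding the benchmark is 0.91 at 85%, 0.43 at 90% and 0.01 at 95%. The verdict depends heavily on the benchmark, which is the input left without a source.

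**The case against.** The strongest reply is that nothing in the protocol calls 85% an all-comer rate. Section 16.1 attaches it first to early-stage and then to intermediate-stage disease, and Section 16.2 intends a comparison with similar patients. It could be a floor set for each group in turn. Because it is an inequality, two groups or two endpoints can both exceed it while differing, for example 93% and 86%. This stands. A reader might infer that 85% is too low for Group I and too high for Groups 2/3, so that selection is credited to surgery. The documents do not support that reading, since without a source the direction of any error is unknown.

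Other points also stand. The ranges in step 4 only return the assumed share and gap. Eligibility (T1–2, N0–2B, limited smoking, no obvious radiologic ECS) already narrows the prognostic spread. A reader might subtract 8 points from 85% to get a PFS benchmark of 77%, but that carries three-year chemoradiotherapy data into a different setting. The two-year recurrence-free figures in Section 2.2 (79% and 86.3%), set beside two-year overall survival of 82% and 80.6%, show no stable gap.

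It can also be said that this is a phase II estimation study, with rates to be determined and reported by pathology group, and with no formal rule turning 85% into a declaration of equivalence. That is fair as to the objectives. It does not answer Section 16.1, which makes equivalence to current regimens the main hypothesis. A common floor, even if met, does not show equivalence to what either group would have achieved on standard care. The Section 16.2 promise of a similar-patient comparison strengthens the point, because no such rate is supplied.

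**Conclusion.** The concern holds in this form. The equivalence hypotheses rest on one unsourced figure, not shown to match the pathology of either Group I or Groups 2/3, and identical for endpoints that are ordered by definition. With no concurrent control, a Group I result above 85% could reflect the selection rule, and PFS below 85% in Groups 2/3 would not show inferiority to standard care.

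For Group I the figure covers OAS and UDC; PFS at >85% appears only for Groups 2/3. LRC already has group-specific thresholds and is outside this criticism.

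No size can be put on the error from the documents. The 86.5–95.5% and 74.5–83.5% ranges, and the pass probabilities, depend on assumed shares, gaps and a success cut-off. They show that the choice of benchmark can decide the conclusion, not that 85% is wrong by a given amount. The matter should be settled before any equivalence conclusion is drawn, because it limits what the trial can claim.

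**What to change.** In Section 16.1, replace the shared >85% with a cited five-year reference rate for each hypothesis: OAS and UDC for Group I, and OAS and PFS for Groups 2/3. Each should come from patients with comparable pathology given standard adjuvant therapy. Use these rates as the posterior thresholds in Section 16.2, which would then deliver the similar-patient comparison that section intends. Where no matched rate can be cited, report the group's estimate with its interval and remove the equivalence claim for that group and endpoint.

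The 85% should not be moved to a pooled analysis of Groups I–III. It would still have no source, and the pooled set mixes surgery alone, radiotherapy and chemoradiotherapy, so it would no longer address surgery alone.

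The cost is a literature extraction and a wording change. Treatment, visits and sample size are untouched. The drawback is that the simple equivalence statement may be lost for one or both groups.

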### 16.2 Sample Size/Accrual Rate

Sample size justification:

The proposed sample size of 100 for Group 1 has been determined to ensure that an upper bound for recurrence may be estimated with adequate precision, defined as within 8-12% of the true recurrence rate. The upper bound is estimated by the posterior probability of recurrence given the observed data, assuming a non-informative beta(1,1) prior distribution. The table below provides the upper 95% bound (from the Bayesian credible interval) assuming the true rate of recurrence is .1,.2,.3,.4, or .5 and 100 patients are studied.

True recurrence	Upper 95% bound
.1	.184
.2	.301
.3	.413
.4	.516

CONFIDENTIAL

This document is confidential. Do not disclose or use except as authorized.

[figure not shown]

.5

.614

The various specific aims outlined in Aim 1 share a common objective: determining rates of important measures of treatment response (progression-free survival, overall survival, local regional control and ultimate disease control) for patients treated with surgery alone and compare them to those expected in patients with similar diagnostic criteria. We will assess this overall objective by using a Bayesian approach to estimate the posterior probability distributions for each respective sub-aim based on observed outcomes. This approach permits estimating probabilities with which a specified rate of interest exceeds a threshold value (e.g.; 50% local regional control, 85% overall survival, etc.)

Our approach begins with the premise that surgery alone offers no improvement in expected outcomes. This is an exact correspondence to a "null hypothesis". We incorporate this assumption through a prior distribution for each suspected rate; for example, for Group I patients we would assume that the rate of local regional control (LRC) at three years is 50%. After the studies are conducted, each respective rate is combined with the "null" prior distribution through Bayes' Theorem to yield the posterior distribution for the rate. The table below depicts simulated results for the posterior LRC ( $\theta$ ) using 100 patients based on two differing assumptions: that LRC at three years is 50% ( $p=0.5$  shown on the left) and 85% ( $p=0.85$  shown on the right).

Our expected sample size of 100 for Group I patients ensures that the inter-quartile range for the estimated probability distributions will extend from approximately 10-12 percentage points. This range is wider for smaller sample sizes (e.g. 30 or 50) but still less than 20 percentage points.

